6.4. Study Intervention Compliance

The date and time of each dose administered will be recorded in the source documents and recorded in the eCRF. The dose of study intervention and study participant identification will be confirmed prior to the time of dosing. Deviations from the prescribed dosage regimen are identifiable via the eCRF.

6.5. Concomitant Therapy

Participants should be instructed to consult authorized site personnel before taking any new medications or supplements during the study. Authorized site personnel should consult the sponsor's medical monitor if there are any questions about concomitant therapies during the study.

Recording of concomitant therapy

Any medication or vaccine (including over-the-counter, bowel preparations or prescription medicines, vitamins, and/or herbal supplements) that the participant is receiving at the time of enrollment or receives during the study must be recorded in the Concomitant Medication eCRF along with

- reason for use
- route of administration, and
- dates of administration, including start and end dates.

Dosage information including dose level and frequency may also be collected when applicable.

Allowed concomitant therapy

Participants are encouraged to maintain their usual medication regimens for concurrent conditions or diseases throughout the study treatment periods, unless those medications are specifically excluded (see [Appendix 7](#)). Participants taking permitted UC concomitant medications are to keep doses stable unless modifications are needed due to AEs, and are to follow the instructions regarding dose stabilization in [Appendix 8](#).

Administration of prohibited UC medications, approved or investigational, constitutes treatment failure. Use of such medications should not be withheld if, in the opinion of the investigator, failure to prescribe them would compromise participant safety. Participants who require a prohibited medication to treat their UC must be discontinued from study drug (Section [7.1.1](#)).

If a concomitant medication is needed to treat an AE or for appropriate medical management, the investigator should base decisions on the participant and clinical factors, considering prohibited medications. A participant who initiates a prohibited medication for a non-UC indication may either discontinue the study drug or discontinue the prohibited medication.

Vaccinations

See [Appendix 7](#) and [Appendix 8](#) for requirements on the timing of vaccinations.

Use of prohibited medications after discontinuation of study drug

At discretion of the investigator, medications listed in [Appendix 7](#) are allowed after a patient discontinues study drug and completes the ETV.

Rescue therapy

This study does not include rescue therapy. Participants who are nonresponders at Week 12 will be assigned to the highest dose of LY3471851 (**CC1** µg), as described in Section 4.1. If these participants remain nonresponders at Week 26, they will be discontinued from study drug and enter post-treatment follow-up period (Section 7.1.1).

Corticosteroid tapering

Participants who enter the study on oral corticosteroid therapy for treatment of their UC should maintain the stable dose of corticosteroid during the entire 12-week induction period. Participants who achieve clinical response at Week 12 will initiate corticosteroid tapering, as described below. For participants who cannot tolerate the corticosteroid taper without recurrence of clinical symptoms, corticosteroid taper may be paused and/or corticosteroid dose may be increased up to the original dose at induction baseline (should not exceed induction baseline dose). In such cases, attempts to reinitiate corticosteroid tapering should be made within 2 weeks of interruption of taper, with a goal to complete tapering no later than Week 26.

Week 12 clinical nonresponders who undergo extended induction with the high dose of LY3471851 will begin corticosteroid tapering if clinical response is achieved at Week 26. For participants who cannot tolerate the corticosteroid taper without recurrence of clinical symptoms, corticosteroid taper may be paused and/or corticosteroid dose may be increased up to the original dose at induction baseline (should not exceed induction baseline dose). In such cases, attempts to reinitiate corticosteroid tapering should be made within 2 weeks of interruption of taper, with a goal to complete tapering no later than Week 40.

The recommended tapering schedule for oral corticosteroids (other than budesonide extended release tablets [budesonide MMX] or beclomethasone dipropionate [gastro-resistant prolonged release tablet]) is as follows.

Dose >10 mg/day prednisone or equivalent: taper daily dose by 5 mg/week until receiving 10 mg/day, and then continue tapering at 2.5 mg/week until 0 mg/day.

Dose ≤10 mg/day prednisone or equivalent: taper daily dose by 2.5 mg/week until 0 mg/day.

The recommended tapering schedule for participants receiving oral budesonide MMX 9 mg/day is to reduce tablets to 9 mg every other day for 2 weeks, followed by 9 mg every third day for 2 weeks, and then discontinue.

The recommended tapering schedule for participants receiving oral beclomethasone dipropionate (gastro-resistant prolonged-release tablet) 5 mg/day is to reduce tablets to 5 mg every other day for 4 weeks, and then discontinue.

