10.7 Appendix 7: Prohibited Medications

This section outlines medications that are prohibited during the treatment phase of the study.

These prohibitions include windows for washout of medications prohibited prior to the screening endoscopy, if applicable.

After a patient discontinues study drug and completes the ETV, use of the medications listed in this appendix is allowed, at discretion of the investigator.

Drug Class	Prohibited Medication Restrictions
Anti-TNF antibodies (for example, infliximab, adalimumab, or golimumab)	Discontinue at least 4 weeks prior to screening endoscopy and prohibited throughout duration of study.
Anti-integrin antibodies (for example, vedolizumab)	Discontinue at least 12 weeks prior to screening endoscopy and prohibited throughout duration of study.
Anti-IL12p40 antibodies (for example, ustekinumab [Stelara®]) or anti-IL-23p19 antibodies (for example, mirikizumab [LY3074828], risankizumab [BI-655066], brazikumab [MEDI-2070], guselkumab [CNTO1959], tildrakizumab [MK-3222]) for any indication, including investigational use	Discontinue at least 4 weeks prior to screening endoscopy and prohibited throughout duration of study.
Agents depleting B or T cells (for example, rituximab, alemtuzumab, or visilizumab)	Discontinue at least 12 months prior to baseline. Participants remain excluded, if evidence of persistent targeted lymphocyte depletion at the time of screening endoscopy.
Immunomodulatory medications, including oral cyclosporine, IV cyclosporine, tacrolimus, mycophenolate mofetil, thalidomide, or JAK inhibitors (for example, tofacitinib or baricitinib)	Discontinue at least 2 weeks prior to screening endoscopy and prohibited throughout duration of study.
Rectally administered 5-ASA therapies (enemas or suppositories)	Discontinue at least 2 weeks prior to screening endoscopy and prohibited throughout duration of study.
Rectally administered investigational preparations for UC such as arsenic preparations	Discontinue at least 4 weeks prior to screening endoscopy and prohibited throughout duration of study.
Rectally administered corticosteroids (enemas or suppositories or foam applications)	Discontinue at least 2 weeks prior to screening endoscopy and prohibited throughout duration of study.
IV corticosteroids	Discontinue at least 2 weeks prior to screening endoscopy. A course of IV corticosteroids is prohibited throughout duration of study.

Drug Class	Prohibited Medication Restrictions

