Systemic corticosteroids for non-UC indications (oral or IV)	Participants requiring systemic corticosteroids for non-UC indications (except corticosteroids to treat adrenal insufficiency) are excluded. Locally administered corticosteroids (for example, inhaled, intranasal, intra-articular, or topical) are allowed.
Oral budesonide standard formulation (that is, not the oral budesonide extended release tablet formulation [budesonide MMX])	Discontinue at least 2 weeks prior to screening endoscopy and prohibited throughout duration of study.
Any investigational therapy (biologic or nonbiologic) not otherwise mentioned in this table	Biologic: Discontinue at least 8 weeks, or 5 half-lives, whichever is longer, prior to screening endoscopy and prohibited throughout duration of study. Nonbiologic: Discontinue at least 4 weeks, or 5 half-lives, whichever is longer, prior to screening endoscopy and prohibited throughout duration of study.
Interferon therapy	Discontinue at least 8 weeks prior to screening endoscopy and prohibited throughout duration of study.
Leukocyte apheresis (leukapheresis, for example, Adacolumn)	Discontinue at least 3 weeks prior to screening endoscopy.
Bacillus Calmette-Guerin (BCG) vaccine	Last vaccination (if any) given at least 12 months prior to baseline. BCG vaccination is prohibited throughout the duration of the study and for 20 weeks after discontinuation of study drug.
Live attenuated vaccines	Last vaccination (if any) given at least 3 months prior to baseline. Live attenuated vaccines are prohibited throughout the duration of the study and for 20 weeks after discontinuation of study drug.

Abbreviations: 5-ASA = 5-aminosalicylic acid; IL = interleukin; IV = intravenous; JAK = Janus Kinase; TNF = tumor necrosis factor; UC = ulcerative colitis.

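### Protocol Section 6.5 and the Appendix 7 header permit every Appendix 7 product after the early termination visit, contradicting the same appendix's 20-week ban on BCG and live attenuated vaccines

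*Protocol*

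**What the plan says.** **The permission.** It is printed twice in the protocol. Section 6.5 (Concomitant Therapy), under the heading on prohibited medications after discontinuation, says that Appendix 7 medications, at the investigator's discretion, "are allowed after a patient discontinues study drug and completes the ETV". The introduction to Appendix 7 (Section 10.7) says: "After a patient discontinues study drug and completes the ETV, use of the medications listed in this appendix is allowed, at discretion of the investigator". Neither sentence carves anything out.

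**The prohibition.** Two rows of the Appendix 7 table extend beyond the end of dosing. For BCG: "BCG vaccination is prohibited throughout the duration of the study and for 20 weeks after discontinuation of study drug". For live vaccines: "Live attenuated vaccines are prohibited throughout the duration of the study and for 20 weeks after discontinuation of study drug".

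**Neighbouring text.** Appendix 7 opens with "This section outlines medications that are prohibited during the treatment phase of the study". The Vaccinations line in Section 6.5 refers the reader to Appendices 7 and 8 "for requirements on the timing of vaccinations". Exclusion criterion 39 (Section 5.2) bars patients who intend to receive BCG or a live attenuated vaccine during the study or within 20 weeks after the last dose.

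**The concern.** The permission covers everything listed in Appendix 7, and BCG and live attenuated vaccines are listed there, in a table of prohibited medications. Read as written, an investigator may give either product as soon as a participant has stopped study drug and completed the ETV, while the row for that product forbids it for 20 weeks.

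What is at stake is participant safety rather than inference. The sponsor set a 20-week restriction on live vaccines after an immune-modulating drug, and two general sentences contradict it. A site that reads only Section 6.5 or the Appendix 7 introduction sees a plain permission, with nothing to prompt a query.

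The ETV triggers the permission, so the conflict concerns participants who stop early. They are an expected group: under Sections 4.1 and 7.1.1, Week 12 nonresponders who are still nonresponders at Week 26 are discontinued from study drug by rule.

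**Working it through.** No statistical figure is involved. The check compares texts, counts rows and works through the timing.

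**1. The two rules side by side**

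| | Permission (Section 6.5; Appendix 7 introduction) | Prohibition (two Appendix 7 rows) |
|---|---|---|
| Products | All medications listed in Appendix 7 | BCG; live attenuated vaccines |
| Applies | From completion of the ETV, after study drug is discontinued | During the study and for 20 weeks after study drug is discontinued |
| Exception stated | None | None |

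They overlap from the ETV to week 20 after discontinuation whenever the ETV takes place within those 20 weeks.

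**2. How many rows are affected**

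The Appendix 7 table has 16 rows. Sorted by the stated end of the prohibition:

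- throughout the study: 11 rows;
- no stated end: 3 rows (B- or T-cell depleting agents, systemic corticosteroids for non-UC indications, leukocyte apheresis);
- 20 weeks after discontinuation of study drug: 2 rows (BCG, live attenuated vaccines).

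11 + 3 + 2 = 16. Only 2 of the 16 rows need an exception.

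**3. Whether another text settles precedence**

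- *The Vaccinations line in Section 6.5.* It leads to Appendix 7, which holds both rules, and to Appendix 8, whose only vaccine row concerns non-live vaccines.
- *Exclusion criterion 39.* It uses the same 20 weeks, but it is an entry criterion about intent and does not govern conduct after discontinuation.
- *The opening sentence of Appendix 7.* It speaks of the treatment phase, which suggests that the permission lifts treatment-phase bans. The two vaccine rows, however, sit in the same table and extend beyond that phase.
- *The recording rule in Section 6.5.* It begins "Any medication or vaccine (including over-the-counter, bowel preparations or prescription medicines" and so names vaccines separately from medications. Appendix 7 nevertheless lists vaccines under a heading about medications.

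Each of these points towards the ban. None states that it prevails.

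**4. Follow-up compared with the ban**

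Table 4 places Visit 801 at least 8 weeks after the last dose and Visit 802 (only for participants positive for anti-HBc at screening) at least 16 weeks after it. If the last dose is taken as the date of discontinuation, the ban outlasts the nominal visits by 20 − 8 = 12 weeks and 20 − 16 = 4 weeks. Part of the ban therefore falls after the last scheduled contact, when the participant and site depend on what the protocol says.

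**The case against.** The strongest reply is that an investigator can comply with both texts. A discretionary permission never requires use, so withholding the vaccine for 20 weeks breaches nothing. The drafting also shows intent. Only the vaccine rows carry the extra 20-week limb, which is written for the time after study drug stops and would do little if the permission overrode it. A literal reading would bar a Week 52 completer, who has no ETV, for 20 weeks while letting an early discontinuer be vaccinated straight after the ETV, and nothing in the protocol suggests that split.

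There are safeguards too: "Participants should be instructed to consult authorized site personnel before taking any new medications or supplements during the study", and site staff are to take questions to the medical monitor. Section 4.2 gives a mean half-life of 8 to 13 days, so 20 weeks (140 days) is 140/13 ≈ 10.8 to 140/8 = 17.5 half-lives, and the later part of the ban lies well beyond the protocol's own washout estimate.

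Most of this stands as evidence that the ban is intended and that the exposure is small. It does not remove the contradiction. Under Section 7.1.1, a participant who stops study drug remains in the study for the ETV and follow-up visits. To have any effect during follow-up, the permission must therefore override the study-long wording of the 11 other rows. It is written to override row-level durations, and nothing tells the reader that it stops short of two of them. Consultation helps only if someone sees a question to ask. The half-life argument does not exclude a longer pharmacodynamic effect, and the documents do not explain the choice of 20 weeks.

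**Conclusion.** The concern holds. Two unqualified permission sentences contradict two rows of the table they refer to, and no text gives an order of precedence. The permission as printed is wrong for 2 of 16 rows.

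This is a minor inconsistency in a participant-safety rule and should be corrected. It affects only participants who discontinue early and complete an ETV, for the time between that visit and week 20 after discontinuation. It has no bearing on the efficacy analysis. The conclusion rests on the current wording and on the inference, well supported but not stated, that the sponsor means the ban to prevail. The documents give neither the expected number of early discontinuers nor any indication of how often such a vaccine would be given, so no count is offered.

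**What to change.** Add one clause to each permission sentence, in Section 6.5 and in the Appendix 7 introduction: *except BCG and live attenuated vaccines, which remain prohibited for 20 weeks as stated in the table.* Leave the two vaccine rows unchanged.

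The cost is one clause in two sentences. The table, design, data collection and analysis stay as they are.

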6.6. Dose Modification

The adaptive design of this study allows the introduction of new dose levels of LY3471851 after the interim analyses for Stage 1, as described in Section 4.1 and Section 6.1. In all stages and study periods, the maximum dose will not exceed **CC1** μg .

No other dose modifications are permitted, except for reasons of immediate participant safety.

6.7. Intervention after the End of the Study

LY3471851 will not be available to participants following completion of the study.

7. Discontinuation of Study Intervention and Participant Discontinuation/Withdrawal

These sections describe reasons for a participant's

- permanent or temporary discontinuation of study drug (Section 7.1), or
- discontinuation (withdrawal) from the study (Section 7.2).

Discontinuation of specific sites or the trial as a whole (“stopping rules”) are handled as part of regulatory, ethical, and trial oversight considerations in Section 10.1.9.

7.1. Discontinuation of Study Intervention

Study drug may be permanently discontinued or temporarily withheld during the study.

Participants who permanently discontinue study drug early will undergo early termination procedures, which include

- an ETV, and
- post-treatment follow-up visits, as shown in the SoA.

7.1.1. Criteria for Permanent Discontinuation of Study Drug

Data collection and safety follow-up when study drug is permanently discontinued

In rare instances, it may be necessary for a participant to permanently discontinue (definitively discontinue) study intervention.

If study intervention is permanently discontinued, the participant will remain in the study to be evaluated at the ETV and post-treatment follow-up visits.

See the SoA for data to be collected at the time of discontinuation and follow-up and for any further evaluations that need to be completed. Safety follow-up is as outlined in the SoA, Section 8.2, and Section 8.3.

Criteria for permanent discontinuation of study drug

Possible reasons for permanent discontinuation of study drug include, but are not limited to, the following:

Participant decision

- The participant requests to discontinue the study drug.

Pregnancy

- The participant becomes pregnant during the study (see Section 8.2.5.1). Pregnant patients **will not** undergo an endoscopy at the ETV.

Safety considerations

- The participant develops any of the following conditions during the study:

- malignancy (except for successfully treated basal or squamous cell skin carcinoma)
 - dysplasia occurring in flat mucosa
 - dysplasia-associated lesion or mass (DALM)
 - HIV infection/acquired immune deficiency syndrome (AIDS)
 - active TB infection or untreated LTBI (Section 7.1.2; Section 8.2.6)
 - HCV RNA positive (Section 8.2.8)
 - HBV DNA positive and clinical assessment consistent with HBV reactivation
 - **Note:** The HBV DNA result is to be confirmed if initial positive test result is positive but below the level of quantification (Section 7.1.2; Section 8.2.7). The participant is to be referred to, evaluated, and managed by a specialist physician with expertise in evaluation and management of viral hepatitis prior to discontinuation of any immunomodulatory and/or immunosuppressive therapy, including study drug. Timing of discontinuation from study drug relative to the initiation of any antiviral treatment for hepatitis is to be based on the recommendation of the consulting specialist physician, in conjunction with the investigator, and aligned with medical guidelines and standard of care.
-
- The participant requires a colectomy, proctocolectomy, or partial colectomy during the study.
 - The investigator, after consultation with the sponsor's designated medical monitor, determines that a systemic hypersensitivity reaction has occurred and is related to study drug administration.
 - The participant has any of the following results on 2 consecutive samples taken at least 48 hours, but no more than 1 week, apart:
 - Total WBC <1000 cells/μL
 - ANC <500 cells/μL
 - ALC <200 cells/μL
 - Hemoglobin <6.5 g/dL
 - The participant develops CRS. In consultation with the Lilly medical monitor, if an AE is deemed possibly or probably due to CRS based on the details and severity of clinical signs and symptoms, time course of symptom onset relative to study drug administration, and if possible, a cytokine panel from a blood sample obtained at the time of the event,

the participant will be discontinued from study treatment, and will continue safety follow-up.

- The participant develops hypereosinophilia.
 - Participants with absolute eosinophil counts >1500 cells/ μ L and signs and/or symptoms of target organ involvement that is not consistent with UC and/or with the participant's UC and medical history will be discontinued from study drug in consultation with the medical monitor. Participants will undergo appropriate medical evaluation, which should take into account the participant's known UC and past medical history according to the participant's history and medical records, including previous imaging, biopsies and laboratory findings. Evaluation of target organ involvement will involve additional diagnostic tests as appropriate, including laboratory tests, imaging (for example, echocardiogram, chest x-ray, CT scan), and biopsies. New onset cardiac, pulmonary, and skin findings in the setting of peripheral eosinophilia will be considered as target organ involvement, unless attributable to other causes.
 - Asymptomatic participants with an absolute eosinophil count >5000 cells/ μ L should have a repeat measurement to confirm the count. If the count is confirmed, the participant will be permanently discontinued from study drug and undergo appropriate medical evaluation.
- The participant has an AE, SAE, or a clinically significant change in a laboratory value that, in the opinion of the investigator, merits the discontinuation of the study drug and appropriate measures being taken.

Hepatic event or liver test abnormality

- Participants who are discontinued from study drug because of a hepatic event or liver test abnormality should have additional hepatic safety data collected via the hepatic eCRF packet. Discontinuation of study drug because of abnormal liver tests should be considered by the investigator when a participant meets 1 of the following conditions after consultation with the sponsor's designated medical monitor (see Section 8.2.9):
 - ALT or AST >8 times ULN
 - ALT or AST >5 times ULN sustained for more than 2 weeks
 - ALT or AST >3 times ULN and TBL >2 times ULN or INR >1.5
 - ALT or AST >3 times ULN with the appearance of fatigue, nausea, vomiting, right upper quadrant pain or tenderness, fever, rash, and/or eosinophilia ($>5\%$)
 - ALP >3 times ULN
 - ALP >2.5 times ULN and TBL >2 times ULN, or

- ALP >2.5 times ULN with the appearance of fatigue, nausea, vomiting, right upper quadrant pain or tenderness, fever, rash, and/or eosinophilia (>5%).

Other reasons for permanent discontinuation of study drug

- The participant
 - scores a 3 for Item 12 (Thoughts of Death or Suicide) on the QIDS-SR16 at any time in the study, or
 - reports suicidal ideation or suicidal behaviors during the study.

Note: A psychiatrist or appropriately trained professional may assist in the decision to discontinue the participant from study drug.

- The participant requires treatment for exacerbation of UC and the treatment involves 1 or more medications at doses higher than those specified in the “dose stabilization” inclusion criterion; for example, the participant requires prednisone >20 mg/day) (see [Appendix 8](#)).
- The participant requires treatment with prohibited medications specified in the “prohibited medications” exclusion criterion, for example, a course of IV corticosteroids or a single dose of infliximab or IV cyclosporine (see [Appendix 7](#)).
- The participant was nonresponder at Week 12 and remains a treatment nonresponder at Week 26.
- Unblinding: If an investigator, blinded site personnel or blinded designees who are performing assessments, or the participant is unblinded to a participant’s treatment assignment because of an emergency unblinding as described in Section 6.3, the participant must be discontinued from the study drug and continue to post-treatment follow-up. In cases where there are ethical reasons to have the participant continue on study drug, the investigator must obtain specific approval from the sponsor’s designated medical monitor for the participant to continue.

Note: The presence or absence of an ISR will not be considered an unblinding event; participants with an ISR may remain in the study and continue to receive study drug, and this will not be considered a protocol deviation.

